11.2 Data Management Plan

A Data Management Plan (DMP) will describe procedures used for data review, data cleaning, issuing and resolving data discrepancies, and database locking. If appropriate, the Sponsor may update the DMP throughout the duration of the clinical investigation. The Sponsor will track and document control all revisions.

Clinical Investigation Plan

11.3 Source Documentation

Regulations and Good Clinical Practice (GCP) require the Investigator to maintain information in the subject's original medical records that corroborates data collected on the CRFs. To comply with these regulatory requirements/GCP, sites should include the following information in the subject record at a minimum and if applicable to the clinical investigation:

- Medical history/physical condition of the subject before involvement in the clinical investigation sufficient to verify CIP entry criteria
- Dated and signed notes on the day of entry into the clinical investigation referencing the Sponsor, CIP number, subject ID number, and a statement that informed consent was obtained
- Dated and signed notes from each subject visit (for specific results of procedures and exams)
- AEs reported and their resolution, including supporting documents, such as discharge summaries, and lab results including documentation of site awareness of SAEs and of investigator assessment of device relationship for SAEs.
- Notes regarding CIP-required and prescription medications taken during the clinical investigation (including start and stop dates)
- Subject's condition upon completion of or withdrawal from the clinical investigation
- Any other data required to substantiate data entered into the CRF

11.4 Case Report Form Completion

Site research personnel trained on the CIP and CRF completion will perform the primary data collection clearly and accurately based on source-documented hospital and/or clinic chart reviews. The Investigator will ensure accuracy, completeness, legibility, and timeliness of the data reported to the Sponsor on the CRFs and in all required reports.

Sites will collect data on all subjects enrolled into the clinical investigation.

Only authorized site personnel will be permitted to enter the CRF data through the EDC system deployed by the Sponsor. The Sponsor will use an electronic audit trail to track any subsequent changes of the entered data.

11.5 Record Retention

The Sponsor and Investigator/Site will archive and retain all documents pertaining to the clinical investigation as per the applicable regulatory record retention requirements and clauses in clinical trial agreements. The Investigator must obtain permission from the Sponsor in writing before destroying or transferring control of any clinical investigation records.

Clinical Investigation Plan

12.0 ETHICAL CONSIDERATION

12.1 Institutional Review Board/Medical Ethics Committee Review and Approval

The Principal Investigator at each investigational site will obtain IRB/EC approval for the CIP and ICF/other written information provided to the patient prior to consenting and enrolling patients in this clinical investigation. The site must receive the approval letter prior to the start of this clinical investigation and provide a copy to the Sponsor.

Sites will submit any amendments to the CIP as well as associated ICF changes to the IRB/EC and written approval obtained prior to implementation, according to each institution's IRB/EC requirements.

No changes will be made to the CIP or ICF or other written information provided to the patient without appropriate approvals, including IRB/EC, the Sponsor, and the regulatory agencies (if applicable).

Until the clinical investigation is completed, the Investigator will advise his/her IRB/EC of the progress of this clinical investigation, per IRB/EC requirements. Written approval must be obtained from the IRB/EC periodically to continue the clinical investigation, or according to each institution's IRB/EC requirements.

Sites will not perform any investigative procedures, other than those defined in this CIP, on the enrolled subjects without the written approval of the IRB/EC and the Sponsor.

13.0 CLINICAL INVESTIGATION CONCLUSION

The clinical investigation will be concluded when:

- All sites are closed AND
- The final report has been provided to investigators or the Sponsor has provided formal documentation of clinical investigation closure and written approval from sites' IRBs/ECs.

14.0 PUBLICATION POLICY

[REDACTED]

[REDACTED]

[REDACTED]

[REDACTED]

Clinical Investigation Plan

15.0 RISK ANALYSIS

15.1 Anticipated Clinical Benefits

[REDACTED]

15.2 Foreseeable Adverse Events and Anticipated Adverse Device Effects

Risks associated with the specified device and procedure are bleeding, hemolysis, endocarditis, infections, thrombus, or thromboembolism, valve dehiscence, unacceptable hemodynamic performance (including: elevated pressure gradients, prosthesis patient mismatch or transvalvular regurgitation), paravalvular leak, hemorrhagic complications secondary to anticoagulation therapy, prosthetic failure (including: pannus ingrowth (NSVD), leaflet fracture/ escape/ split/ dislodgement, and entrapped leaflet/ stuck valve/ leaflet immobility, thrombocytopenia, heart block requiring pacemaker implant, adjacent cardiac structure interference, stroke, heart failure, myocardial infarction, or death as described in the IFU. Any of these complications may require reoperation or explantation of the device. There may be risks related to the device under investigation that are unknown at present. Likewise, the exact frequency of the risk may be unknown.

15.3 Residual Risks Associated with the Device Under Investigation, as Identified in the Risk Management Report / Risk Analysis Report

Risk analysis of the Regent MHV device has been performed in accordance with the Risk Analysis Plan [REDACTED] and Design Failure Mode Effect Analysis [REDACTED] to systematically identify potential hazards associated with the design and use of this device. Based upon bench testing and prior Abbott-sponsored clinical study data, all risks have been identified and mitigated as far as possible through application of appropriate controls and inspections and determined to be within acceptable levels.

Residual risks are likewise disclosed in the IFU in the form of clear instructions of what actions to take or to avoid, to avoid a hazardous situation of harm from occurring (contra-indications, warnings, and precautions). The anticipated AEs disclosed in the IFU provide further information to enable the user, and potentially the subject, to make an informed decision that weighs the residual risk against the benefit of using the device.

15.4 Risks Associated with Participation in this Clinical Investigation

[REDACTED]

[REDACTED]

[REDACTED]

Clinical Investigation Plan

[REDACTED]

[REDACTED]

15.5 Steps Taken to Control or Mitigate Risks

In-depth recommendations, special precautions, and instructions regarding device handling, device placement and system removal are included in the IFU.

It is also stated in the IFU that the device should be used by or on order of a physician. This statement is interpreted to mean that the physician users are expected to be aware of the known and foreseeable safety risks associated with the use of the devices, including the surgical and/or non-surgical treatment of these conditions.

Risks associated with the use of the device under investigation are minimized through device design, investigator selection and training, and study monitoring to ensure adherence to the protocol. Sites will report all adverse events and device deficiencies to the Sponsor, and the Sponsor will monitor internally for safety surveillance purposes.

15.6 Risk to Benefit Rationale

Regent MHVs have been used for more than 20 years with good clinical outcomes. Surgical interventions including aortic root replacement with Regent MHVs are indicated in subjects with complex aortic root pathologic disease. The clinical benefits of these Regent MHVs include reduction in symptoms of aortic valve disease, improvement in hemodynamics, and longer life expectancy with improved quality of life. Regent MHVs have shown a lower rate of device failure, as well as greater durability and less structural deterioration over time than bio-prosthetic valves. Anticoagulant therapy is routinely used in subjects implanted with a Regent MHV. The use of anticoagulants increases the risk of bleeding; however, in clinical data observed from the literature, the risk of bleeding and thromboembolism associated with the MHV devices was low for subjects in whom the use of both biological and mechanical Regent MHV is possible. The clinical evidence and post-market data support a positive risk-to-benefit ratio in subjects receiving a Regent MHV for aortic root replacement.

Clinical Investigation Plan

APPENDIX I: ABBREVIATIONS AND ACRONYMS

Abbreviation	Term
AE	Adverse Event
CIP	Clinical Investigation Plan
CRF	Case Report Form
DMP	Data Management Plan
EC	Ethics Committee
EDC	Electronic Data Capture
GCP	Good Clinical Practice
ICF	Informed Consent Form
IFU	Instructions For Use
INR	International Normalized Ratio
IRB	Institutional Review Board
KM	Kaplan-Meier
MHV	Mechanical Heart Valve
NMPA	National Medical Products Administration
NYHA	New York Heart Association
OPC	Objective Performance Criteria
PI	Principal Investigator
PMCF	Post-market Clinical Follow-up
PVL	Paravalvular Leak
TEE	Transesophageal Echocardiography
TTE	Transthoracic Echocardiography
SAE	Serious Adverse Event
SOC	Standard of Care
USA	United States of America (same as US)
VHD	Valvular Heart Disease

Clinical Investigation Plan

APPENDIX II: DEFINITIONS

The following definitions for primary and descriptive endpoint events will be used in this investigation. These definitions are taken from the Akins *et al.*²⁵ guidelines for adverse event reporting after cardiac valve interventions referenced in ISO 5910:2018 “Cardiovascular implants and extracorporeal systems—Cardiac valve repair devices.” Note that the Akins *et al.* definition of embolism is limited to thromboembolism, which is the term used in the text of the CIP. Similarly, the Akins *et al.* definition of a bleeding event is limited to major bleeding and this terminology is used in the CIP text.

All-cause Mortality: All-cause mortality includes all deaths from any cause after a valve intervention.

Embolism: Embolism is any embolic event that occurs in the absence of infection after the immediate perioperative period. Embolism may be manifested by a neurologic event or a noncerebral embolic event. A neurologic event includes any central, new neurologic deficit, whether temporary or permanent and whether focal or global, that occurs after the patient emerges from anesthesia. A noncerebral embolic event is an embolus documented operatively, at autopsy, or clinically that produces signs or symptoms attributable to complete or partial obstruction of a peripheral artery. Intraoperative myocardial infarctions are not counted. Postoperative myocardial infarction is also not counted unless the infarction is caused by a coronary embolus (as detected by operation, autopsy, or clinical imaging). Emboli consisting of non-thrombotic material (e.g., atherosclerosis, myxoma) are not counted.

Bleeding Event: A bleeding event is any episode of major internal or external bleeding that causes death, hospitalization, or permanent injury (e.g., vision loss) or necessitates transfusion. Major bleeding unexpectedly associated with minor trauma should be reported as a bleeding event, but bleeding associated with major trauma or a major operation should not. Bleeding events are reported for all patients regardless of whether they are taking anticoagulants or antiplatelet drugs. Although total bleeding events must be reported, bleeding events can also be reported separately for those who are taking anticoagulants or antiplatelet agents and those who are not.

Operated Valve Endocarditis: Operated valve endocarditis is any infection involving a valve on which an operation has been performed. The diagnosis of operated valvular endocarditis is based on one of the following criteria: (1) reoperation with evidence of abscess, paravalvular leak, pus, or vegetation confirmed as secondary to infection by histologic or bacteriologic studies; (2) autopsy findings of abscess, pus, or vegetation involving a repaired or replaced valve; or (3) in the absence of reoperation or autopsy, meeting of the Duke Criteria for endocarditis. Positive blood cultures are not required for the diagnosis of operated valve endocarditis. Culture-negative endocarditis should refer only to negative blood culture results and not just the absence of any proof of infection. Morbidities associated with active infection, such as valve thrombosis, thrombotic embolus, bleeding event, or paravalvular leak, are included under this category, but not counted in other categories of morbidity.

Clinical Investigation Plan

Reintervention: Reintervention is any surgical or percutaneous interventional catheter procedure that repairs, otherwise alters or adjusts, or replaces a previously implanted prosthesis or repaired valve. In addition to surgical reoperations, enzymatic, balloon dilatation, interventional manipulation, repositioning, or retrieval, and other catheter-based interventions for valve-related complications are also considered reinterventions. Indications for reintervention must be reported. Open surgical and percutaneous catheter reinterventions should be listed separately.

Valve Thrombosis: Valve thrombosis is any thrombus not caused by infection attached to or near an operated valve that occludes part of the blood flow path, interferes with valve function, or is sufficiently large to warrant treatment. Valve thrombus found at autopsy in a patient whose cause of death was not valve-related or found at operation for an unrelated indication should also be counted as valve thrombosis.

Valve-Related Mortality. Valve-related mortality is any death caused by structural valve deterioration, nonstructural dysfunction, valve thrombosis, embolism, bleeding event, or operated valve endocarditis; death related to reintervention on the operated valve; or sudden, unexplained death. Deaths caused by heart failure in patients with advanced myocardial disease and satisfactorily functioning cardiac valves are not counted. Specific causes of valve-related deaths should be reported.

NYHA Functional Classification^{26,27}

Class	Patient Symptoms
I	No limitation of physical activity. Ordinary physical activity does not cause undue fatigue, palpitation, dyspnea (shortness of breath).
II	Slight limitation of physical activity. Comfortable at rest. Ordinary physical activity results in fatigue, palpitation, dyspnea (shortness of breath).
III	Marked limitation of physical activity. Comfortable at rest. Less than ordinary activity causes fatigue, palpitation, or dyspnea.
IV	Unable to carry on any physical activity without discomfort. Symptoms of heart failure at rest. If any physical activity is undertaken, discomfort increases.

Clinical Investigation Plan

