5.3.1 Inclusion Criteria

1. Patient is eligible to be implanted with Regent to replace a native or prosthetic aortic valve per Regent's IFU
2. Subject will be ≥ 18 years of age at time of being consented
3. Subject provides written informed consent prior to any clinical investigation-specific procedure.

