5.3.2 Exclusion Criteria

1. Subject is unable to tolerate anticoagulation therapy
2. Subject has active endocarditis
3. Subject is currently participating in another clinical investigation which may interfere with the effectiveness of anticoagulation therapy
4. Pregnant or nursing subjects and those who plan pregnancy during the clinical investigation follow-up period. Women of child-bearing potential must have a documented negative pregnancy test within one week prior to enrollment
5. Subject has anomalous anatomy or medical, surgical, psychological or social history or conditions that, in the Investigator's opinion, could limit the subject's ability to participate in the clinical investigation or to comply with follow-up requirements of the clinical investigation results
6. Subject is unable to read or write or has a mental illness or disability that impairs their ability to provide written informed consent
7. Subject's life expectancy is less than 1 year in the opinion of the Investigator

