6.2 Index Procedure

Subjects that meet inclusion and exclusion criteria and provide written informed consent but do not undergo a Regent MHV implant within 60 days of enrollment will be withdrawn without further follow-up required. The following information will be collected during the index procedure.

- Procedure characteristics (e.g., surgeon, access approach, CPB time)
- Regent MHV implant
- Concomitant procedures
- Adverse Events
- Cardiac medications

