7.3 Adverse Event and Device Deficiency/Device Malfunction Reporting

7.3.1 Adverse Event Reporting

Safety surveillance and reporting starts as soon as the subject is enrolled in the clinical investigation. Adverse events will not be collected for screen failure subjects. Safety surveillance and reporting will continue until sites perform the last follow-up visit, the subject is deceased, the subject concludes participation in the clinical investigation, or the subject withdraws from the clinical investigation. Sites should update additional information regarding an adverse event on the appropriate CRF.

Unchanged, chronic, non-worsening or pre-existing conditions are not AEs and should not be reported.

For the purpose of this trial, the following adverse event types will be reported:

- Adverse events considered related to the implanted Regent MHV
- All serious adverse events

Clinical Investigation Plan

In addition, the following endpoint-related adverse events meeting the Akins²⁵ criteria defined in Appendix II will be reported regardless of seriousness or relatedness:

- Death – all-cause and valve-related mortality
- Reinterventions of the replaced valve
- Major bleeding
- Thromboembolism
- Valve thrombosis
- Endocarditis (operated valve)
- Major paravalvular leak

The Investigator will assess the events for relationship to the device and relationship to the procedure.

The Sponsor will provide an offline form to allow the Investigator to report SAEs in the event the entry cannot be made in the EDC. This does not replace the EDC reporting system. Sites must still enter all information in the EDC system as soon as feasible.

SAE Reporting

The Investigator must report all SAEs to the Sponsor as soon as possible but no later than outlined below.

Clinical Site	Reporting timelines
All Sites	Investigators must report SAEs to the Sponsor no later than 24 hours from the day the site personnel became aware of the event or as per the investigative site's local requirements, if the requirement is more stringent than those outlined.

Sites must record the date the site staff became aware that the event met the criteria of an SAE in the source document. The Investigator will report the SAE to the local IRB/EC according to the institution's IRB/EC reporting requirements.

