### 2.7 Subgroups for Analysis

No subgroup analyses are planned for this clinical investigation.

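### Endocarditis, valve thrombosis and, through them, valve-related death are not limited to the study Regent, so events on another operated valve can enter the primary safety endpoint and two descriptive rates

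*Protocol*

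**What the plan says.** **Eligibility.** CIP 5.3.1 requires that "Patient is eligible to be implanted with Regent to replace a native or prosthetic aortic valve per Regent's IFU". None of the seven exclusions in CIP 5.3.2 names another prosthesis, a repaired valve or concomitant valve surgery. The closest is a judgement clause: "Subject has anomalous anatomy or medical, surgical, psychological or social history or conditions that, in the Investigator's opinion, could limit the subject's ability to participate". CIP 3.2 says that the criteria are intentionally broad. CIP 6.2 lists "Concomitant procedures" among the data to collect, with no limit on type, and Table 2 has a matching row.

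**Definitions.** CIP Appendix II applies to primary and descriptive endpoint events.
- Endocarditis: "Operated valve endocarditis is any infection involving a valve on which an operation has been performed".
- Thrombosis: "Valve thrombosis is any thrombus not caused by infection attached to or near an operated valve".
- Reintervention: "Reintervention is any surgical or percutaneous interventional catheter procedure that repairs, otherwise alters or adjusts, or replaces a previously implanted prosthesis or repaired valve".
- Valve-related mortality includes death caused by thrombosis, endocarditis, embolism or bleeding, death related to reintervention on the operated valve, and sudden unexplained death.

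**Body text.** CIP 7.3.1 lists "Reinterventions of the replaced valve" for reporting. CIP 1.1.2 and 8.2.2 also speak of the replaced valve, and CIP 4.1 of reoperation on the MHV. Endocarditis carries only the label of operated valve (CIP 4.2 and 7.3.1, SAP 1.4.3).

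**Analysis.** SAP 3.5 expresses the descriptive rates per valve-year, without saying which valves supply the years, and compares five of them with twice the ISO OPC. SAP 2.7 states: "No subgroup analyses are planned for this clinical investigation".

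**The concern.** Take a subject with a Regent in the aortic position and a prosthesis in the mitral position. Under Appendix II as written, thrombosis of the mitral prosthesis is a valve thrombosis event, and a death from it is a primary safety event. The device-relationship assessment in CIP 7.3.1 does not remove it, because the listed endpoint events are reported whatever their relatedness.

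The results would then describe a mixture of the Regent and other prostheses or repairs, while the objective and the acceptance criteria concern the Regent. The rare-event rates are the most exposed, because the number of events allowed is very small. The unspecified denominator adds to the doubt. Events on a second valve divided by Regent years raise the rate. Adding that valve's years as well yields a mixed rate, which could be higher or lower than the Regent's own.

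**Working it through.** There is no stated figure to reproduce: the basis for the sample size is redacted, and the point turns on wording. The arithmetic below is for scale only.

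**Inputs from the documents.** 200 implanted subjects (CIP 8.3, SAP 2.4); 5 years of follow-up (CIP 3.0); OPC 0.1% per valve-year for thrombosis and 0.3% for endocarditis, each compared at twice its value (SAP 3.5).

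**Assumptions, not in the documents.** A share f of 5-30% of subjects has a second operated valve. Its event rate is r times the Regent's, with r = 1 or 2. The Regent's true rate equals the OPC. Follow-up is complete, and the denominator is Regent valve-years.

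**Weight of one event.** Maximum exposure = 200 x 5 = 1000 valve-years, so one event is 1/1000 = 0.1% per valve-year.
- Thrombosis: allowance = 2 x 0.1% x 1000 = 2 events; one event uses 1/2.
- Endocarditis: allowance = 2 x 0.3% x 1000 = 6 events; one event uses 1/6.

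Fewer valve-years would make these shares larger.

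**Chance of exceeding twice the OPC.** The event count is taken as Poisson with mean λ = OPC x 1000 x (1 + f x r). The limit is exceeded at more than 2 thrombosis events or more than 6 endocarditis events.

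| f | Thrombosis, r = 1 | Thrombosis, r = 2 | Endocarditis, r = 1 | Endocarditis, r = 2 |
|---|---|---|---|---|
| 0 | 0.080 | 0.080 | 0.034 | 0.034 |
| 5% | 0.090 | 0.100 | 0.042 | 0.051 |
| 10% | 0.100 | 0.121 | 0.051 | 0.073 |
| 20% | 0.121 | 0.167 | 0.073 | 0.133 |
| 30% | 0.143 | 0.217 | 0.101 | 0.209 |

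For example, endocarditis with f = 30% and r = 1 gives λ = 0.003 x 1000 x 1.3 = 3.9, an apparent rate of 0.39% per valve-year, and P(more than 6) = 0.101. The row f = 0 is what remains when only Regent events count.

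**Primary safety endpoint.** Its criterion is redacted, so no probability can be given. As a crude proportion without censoring, one death is 1/200 = 0.5 percentage points of 5-year freedom.

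**Reintervention, side by side.** Appendix II covers any previously implanted prosthesis or repaired valve. CIP 1.1.2, 7.3.1 and 8.2.2 restrict it to the replaced valve, and CIP 4.1 ties reoperation to the MHV. The body text points to the study valve, and the appendix does not follow. After a double replacement, even the replaced valve is not a unique description.

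**The case against.** A reader might infer that events on other valves do enter both primary endpoints and will decide whether the criteria are met. The documents do not support that, for four reasons.

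1. For the performance endpoint, four places in the body text already point to the Regent. What remains is an inconsistency with Appendix II.
2. The IFU, which governs eligibility, is not among the documents. The text on analysis populations and primary analyses (CIP 8.1 to 8.2.2) is redacted in whole or part, and SAP 2.1.1 shows no text. A restriction there cannot be ruled out, so the right word is can. In a study of aortic replacement, the operated valve may also naturally be read as the study valve, although the articles used for endocarditis and thrombosis do not say so.
3. The share of multi-valve subjects is assumed. At equal rates the probabilities move modestly, and at 5% very little.
4. The comparisons are descriptive, and CIP 8.6 rules out formal testing. With Regent valve-years as denominator, extra events count against the device.

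The plan also records causes of valve-related death, indications for reintervention and concomitant procedures, so part of the attribution could be rebuilt.

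A further objection concerns the remedy. SAP 2.10 refers to site-reported valve-related deaths, and the readable text describes no independent adjudication. Removing deaths according to which valve is blamed could favour the device in an open single-arm study. That objection stands, and the fix allows for it.

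None of this removes the core point: the readable rules for endocarditis, thrombosis and valve-related death are not limited to the Regent.

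**Conclusion.** The point holds for the primary safety endpoint and for the endocarditis and valve thrombosis rates: as written, events on another operated valve can count. For reintervention and the primary performance endpoint it is a mismatch between Appendix II and the body text that must be reconciled; contamination of that endpoint is not shown. Bleeding, thromboembolism and all-cause death are patient-level events, so the operated-valve wording is not the issue there. A bleed or embolus simply may not be attributable to one valve.

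The weight of a single event (1/2 and 1/6 of the allowance) follows from the documents' own figures at full follow-up. The shift in probability rests on the assumed 5-30% share, the assumed rate on the second valve and a Regent rate equal to the OPC. It is modest at equal rates and reaches about 0.21-0.22 only at a 30% share with twice the rate. The change should be made because it is cheap, and because event location is harder to recover after five years.

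**What to change.** 1. In Appendix II and SAP 3.5, add a counting rule: endocarditis, valve thrombosis and reintervention count toward the Regent rates only when they involve the study Regent in the aortic position, and valve-years are Regent valve-years. This also aligns the reintervention definition with the body text and removes the ambiguity after a double replacement.
2. Add a field for the valve involved to the event CRF, if it is not already there (the forms are supplied separately), and list events on other valves separately.
3. Apply the rule to the rates only. Keep every death that meets the present valve-related definition in the main primary safety result, and keep emboli and bleeds that cannot be located to one valve in their main rates. Unadjudicated attribution then cannot favour the device.
4. Add one sensitivity table of the two primary endpoints and the valve-event rates in subjects with no other operated or prosthetic valve, identified from medical history and concomitant procedures.

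**Cost.** Wording changes, one CRF field and one table. The table is less precise than the main result and needs one stated exception to SAP 2.7 and CIP 8.5. Valve location remains site-reported. The main safety result can still include a death due to another valve; the sensitivity table shows whether that matters.
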